**Justification for proposed analyses:**

The original analysis excluded 48% of initiators (51% of 11 mg QD initiators and 40% of 5 mg BID initiators) due to lack of eligible follow-up. When incorporating the most updated follow-up information, the exclusion rate will be reduced to 33%. In addition to the raw reduction in exclusion rate, the rates will be balanced between initiation dose groups (34% of 11 mg QD initiators excluded compared to 33% of 5 mg BID initiators excluded).

Additionally, presenting the rate of achievement of MCID in CDAI while assuming that all ineligible initiators do not achieve MCID will attempt to determine the potential effects of a theoretical worst-case scenario.

CCI

[Redacted]

CCI

[Redacted]

Where currently we only consider visits between 3 and 9 months as eligible to be the six-month follow-up visit, we will widen the window of time defining a six-month follow-up visit, considering any visit within the first year after initiation as eligible to be the six-month follow-up visit. This altered definition will create a larger analysis cohort (Table 3); therefore, we will replicate all analyses performed CCI [Redacted] using this new sample of 689 patients.

CCI

[Redacted]

CCI

[Redacted]

[Redacted]

CCI

[Redacted]

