### Background:

Tofacitinib (tofa) 11 mg QD was approved in February 2016. It is hypothesized that this formulation will behave similarly to the Tofacitinib 5 mg BID dosage in terms of efficacy.

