Analysis: We will update the sample selection figure to reflect the sample derived from the end of September 2018 version of the registry. Reasons for exclusion will be detailed and will include: initiated treatment too late (i.e. after 3/31/2018) and so had not reached time for 6 month visit, no 6 month visit despite having initiated treatment

longer than 6 months ago, no valid CDAI at initiation, and no valid CDAI at 6 months despite attending visit.

	5 mg BID (N/%)	11 mg QD (N/%)
Initiated after 3/31/2018 (not reached 6 months)		
No 6 month visit		
No valid CDAI at initiation		
No valid CDAI at attended 6 month visit		

In addition to the analyses, we will provide an interpretation of the results, including thoughts on the reasons for the listed difference. We will also assess the potential biases that may be introduced into the analyses due to the exclusion criteria.

**Objective 3:** Repeat the primary analyses (Tables 1 – 3\_adj) using a propensity score trimmed population.

To ensure the adjusted analyses do not extrapolate due to the use of dissimilar patients, the propensity score which was previously used to match patients can be used to trim the population of the initiations for which there is no similar initiation in the other group – carrying out the multivariable adjustment for patients on “common support” across the covariates of interest. The propensity score distribution will be examined in both populations and each population will be trimmed for extreme values: patients in one group with propensity scores higher or lower than scores in the other group will be “trimmed” (i.e., excluded from analyses). Only patients with scores overlapping both distributions will be included in the analysis.

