**Proposed Analyses:**

1. Repeat all analyses (Tables 1 – NI) using more recent data

Of the previously defined cohort of 869 tofacitinib initiators (611 initiators of 11 mg QD, and 258 initiators of 5 mg BID) who initiated on or after 2016/02/01, 306 patients (245 initiators of 11 mg QD, and 61 initiators of 5 mg BID) had no available follow-up visits post-initiation using the original 2018/09/30 version of the RA registry, and so were excluded from analysis. In order to remedy the high proportion of initiators with no follow-up, we will consult the most recent data available (RA registry version 2019/08/31) in order to provide the most complete understanding of the availability of follow-up for these patients.

Preliminary investigations indicate that 117 of these 306 initiators have an eligible six-month follow-up visit available and can be included in further analyses (Appendix Table). With the addition of these patients, we would proceed to further analyses with 401 (66%) out of the 611 initiators of 11 mg QD, and 172 (67%) out of the 258 initiators of 5 mg BID (Table 2). After updating the eligible sample and replicating all analyses, the report previously delivered on CCI [REDACTED] will be re-created. (Note: final analyses will also require valid CDAL measurements at initiation and six-month follow-up, which will exclude a small number of patients from these cohorts)

Table 2. Tofacitinib initiators' eligibility status categories by initiation dose, using 2019/08/31 version of RA database

	All Initiators	11 mg QD	5 mg BID
After 1/31/2016	869	611	258
No follow-up	113 (13%)	79 (13%)	34 (13%)
First follow-up not during first year	67 (8%)	51 (8%)	16 (6%)
Follow-up within first year BUT no six-month visit	116 (13%)	80 (13%)	36 (14%)
Eligible six-month visit	573 (66%)	401 (66%)	172 (67%)

2. Perform sensitivity analysis of primary outcome

Using the updated eligible cohort detailed in Table 2 above, 34% of initiators will remain ineligible for analysis. We will present an additional table similar to Addendum Full Table 2 CCI which will include all 869 initiators of 11 mg QD and 5 mg BID, treating those who are not eligible due to lack of six-month follow-up visit as not achieving MCID in CDAI.

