**Proposed analyses:**

1. Compare eligible initiators to non-eligible initiators across several key characteristics at initiation

We will create a baseline table comparing eligible (the green highlighted row in Table 2 above) and non-eligible (the white, red, and orange highlighted rows in Table 2 above) initiators. The table will include key characteristics: sex, age, duration or RA, line of therapy, and CDAI, and comparisons will be made using standardized differences.

CCI

[Redacted]

CCI [Redacted]

[Redacted]

CCI [Redacted]

[Redacted]

CCI [Redacted]

[Redacted]

[Redacted]

CCI [Redacted]

[Redacted]

CCI

CCI

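### Coding missing initiators as failures in both arms is a worst case for each arm's response rate, but not for the QD–BID comparison

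*SAP*

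**What the plan says.** Item 2 of the SAP section Proposed Analyses (2019 data refresh) adds a table covering the full cohort of 869. Its imputation rule is given as "treating those who are not eligible due to lack of six-month follow-up visit as not achieving MCID in CDAI". The rule is the same in both arms. The next section, Justification for proposed analyses, says that presenting the MCID rate in this way "will attempt to determine the potential effects of a theoretical worst-case scenario".

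The table is to follow the addendum version of Table 2. Table 2 sets the QD response rate beside the BID rate and reports a p-value for the comparison.

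The SAP Background gives the hypothesis: "It is hypothesized that this formulation will behave similarly to the Tofacitinib 5 mg BID dosage in terms of efficacy".

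Three other visible items bear on the missing patients:

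- a wider visit window, "considering any visit within the first year after initiation as eligible to be the six-month follow-up visit", giving 689 patients;
- a baseline table described as "Compare eligible initiators to non-eligible initiators across several key characteristics at initiation";
- a promise under Objective 2 of the addendum: "We will also assess the potential biases that may be introduced into the analyses due to the exclusion criteria".

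**The concern.** Setting every missing patient to failure gives the lowest possible response rate in each arm. The study, however, asks whether two regimens differ, and it expects them to be similar. For that question the unfavourable scenario is that missing patients responded differently in the two arms. The planned rule excludes this scenario, because it gives both arms the same missing response rate of zero.

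A reader told that a worst case still shows little difference may take it as evidence that similarity is robust to the missing third. The table cannot show that. Depending on the true outcomes, it can make the arms look more alike or less alike than they are. It can also change the test result through the imputation alone.

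**Working it through.** **Inputs.** Counts are from Table 2 of the SAP section Proposed Analyses (the eligibility table). Response rates are not given there, so I assume values around the 50% planning rate in the SAP power calculations.

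| | QD | BID | All |
|---|---|---|---|
| Initiators | 611 | 258 | 869 |
| Six-month visit | 401 | 172 | 573 |
| No six-month visit | 79+51+80 = 210 | 34+16+36 = 86 | 296 |
| Visit within one year | 401+80 = 481 | 172+36 = 208 | 689 |
| No visit within one year | 130 | 50 | 180 |

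**Reproducing the SAP's figures.** 210/611 = 34.4% and 86/258 = 33.3%, matching the stated 34% and 33%. The one-year cohort of 689 also reproduces; it leaves 180/869 = 20.7% with no outcome.

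**What the planned rule does.** Imputed rate = observed rate × retention, with retention rQ = 401/611 = 0.656 and rB = 172/258 = 0.667. The tabulated difference is therefore 0.656·pQ − 0.667·pB. Confidence intervals are Wald, on 401/172 before imputation and 611/258 after; they treat imputed values as data.

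| Observed QD vs BID | Patients with a visit, points (95% CI) | Planned table, points (95% CI) |
|---|---|---|
| 35% vs 50% | -15.0 (-23.8 to -6.2) | -10.4 (-17.0 to -3.7) |
| 45% vs 50% | -5.0 (-13.9 to 3.9) | -3.8 (-10.6 to 3.0) |
| 241/401 vs 86/172 (60.1% vs 50.0%) | +10.1 (1.2 to 19.0), p = 0.025 | +6.1 (-0.8 to 13.0), p = 0.089 |

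The p-values are chi-squared without continuity correction.

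With BID at 50%, observed differences of -15, -10, +10 and +15 points shrink by 31%, 29%, 40% and 38%. The shrinkage is on the absolute scale: for 35% vs 50% the rate ratio moves only from 0.70 to 0.230/0.333 = 0.69. Small QD deficits do not shrink. The tabulated difference is 0.656·d − 0.0052, so a deficit grows when it is below 0.0052/0.344 = 1.5 points.

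**Range for the comparison.** Take 50% observed in both arms.

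- Planned table: 32.8% vs 33.3%, difference -0.5.
- Missing QD fail, missing BID respond: 32.8% vs 66.7%, difference -33.9.
- Missing QD respond, missing BID fail: 67.2% vs 33.3%, difference +33.9.
- Same two bounds in the 689-patient cohort: -20.3 and +20.3.

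The planned result lies near the middle of the possible range, not at its edge.

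**Break-even.** Keep 50% observed in both arms and let missing BID respond at 50%. Solve 0.5·rQ + mQ·(1 − rQ) − 0.5 = D for mQ, the response rate among missing QD.

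| Target difference D | mQ, 573 with a six-month visit | mQ, 689 with a visit in one year |
|---|---|---|
| -5 points | (0.450 − 0.328)/0.344 = 35.5% | (0.450 − 0.394)/0.213 = 26.5% |
| -10 points | (0.400 − 0.328)/0.344 = 20.9% | (0.400 − 0.394)/0.213 = 3.0% |

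**The error can run the other way.** Observed 35% vs 50%, missing QD at 65%, missing BID at 35%: QD = 0.656×0.35 + 0.344×0.65 = 45.3%; BID = 0.667×0.50 + 0.333×0.35 = 45.0%. The true difference is +0.3, while the planned table shows -10.4.

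The few patients with a visit but no valid CDAI are ignored throughout.

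**The case against.** The strongest reply is textual. The sentence in the SAP speaks of presenting the rate, says only that it will attempt to show a worst case, and never calls the table a bound on the difference. Read that way the label is correct. This stands for the arm-specific rates, but the table is laid out as a QD–BID comparison with a p-value, so the comparative reading is the natural one.

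Second, the relevant sections are heavily redacted. The SAP refers to tables running up to one labelled NI and cites a guideline on non-inferiority margins, so at least one comparative analysis is probably hidden, perhaps with a margin. This limits the point to the visible text, and a cross-reference would answer it if an arm-specific analysis exists.

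Third, symmetric non-responder imputation is a recognised analysis. It extends the SAP's existing rule for patients who discontinue or switch. The data refresh has also brought the exclusion rates from 51% vs 40% to 34% vs 33%, with similar reasons in both arms. All this is to the plan's credit. But equal amounts of missing data do not imply equal outcomes among the missing, and the balance is what makes the symmetric rule little more than a rescaling. The one-year window reduces the gap without closing it, the baseline comparison uses observed characteristics only, and the method of the promised bias assessment is not specified.

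Fourth, the response rates are illustrative, the example that crosses 0.05 was chosen to show that this can happen, and the extreme bounds mostly restate how much is missing. All true, which is why the break-even values matter more than the extremes.

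**Conclusion.** The concern holds and should be fixed. The planned table is the minimum for each arm's response rate but does not bound the comparison. On assumed rates it shrinks absolute differences of 10 to 15 points by 29 to 40%. With 50% observed in both arms it reports about -0.5 points, whereas missing outcomes alone could move the difference from -33.9 to +33.9 (from -20.3 to +20.3 with the one-year window). Less extreme departures also matter: a 35.5% response among missing QD against 50% among missing BID gives -5 points overall.

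The counts are the SAP's own; every response rate is an assumption. The primary estimate is not affected. The conclusion applies to the visible text only.

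**What to change.** - Call the table non-responder imputation in both arms, and do not present it as a worst case for the comparison.
- Add the two opposite-direction imputations: missing QD fail with missing BID respond, and the reverse.
- Add a tipping-point grid over the two arms' missing response rates, for the 573 patients with a six-month visit and ideally for the 689-patient cohort. Report which combinations move the difference and its 95% CI past the level that the sponsor regards as dissimilar. Base the interpretation on the grid, not on the extremes.
- If a redacted section already contains an arm-specific analysis, refer to it here.
- As a minor clarification, state how initiators with a visit but no valid CDAI are counted. Item 2 imputes for a missing visit, while item 1 treats valid CDAI as a separate requirement "which will exclude a small number of patients from these cohorts". The conclusion above does not depend on this.

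The cost is a change of wording and one extra table from data already in hand, with a sentence explaining that the extreme bounds are wide because they mainly reflect the amount missing.

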9.2.1. Inclusion Criteria

Patients must meet all of the following inclusion criteria to be eligible for inclusion in the study:

1. All US Corrona RA Registry patients who initiated tofacitinib 5 mg BID or tofacitinib 11 mg QD after it became available in February 2016.

2. Patients must have a follow-up visit at 6 months (+/- 3 months) after tofacitinib initiation. These 6 month visits are part of routine practice and is not associated with this protocol.
3. Patients must have a valid clinical disease activity index (CDAI) at initiation and at 6-month follow-up visit.

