### Secondary Outcomes for Overall Aim:

- Change from baseline to 6 month follow-up CDAI (as a continuous variable)
- Achievement of Remission (CDAI $\leq$ 2.8) at 6 month follow-up (among all)
- Achievement of Remission (CDAI $\leq$ 2.8) at 6 month follow-up (among those that were not in remission at initiation)
- Achievement of Low Disease Activity (LDA) (CDAI $\leq$ 10) at 6 month follow-up (among all)
- Achievement of Low Disease Activity (LDA) (CDAI $\leq$ 10) at 6 month follow-up (among those that were not in remission or LDA at initiation)
- Achievement of improvement from baseline to 6 month follow-up in modified HAQ (mHAQ) of 0.25 (as a dichotomous variable)
- Change from baseline to 6 month follow-up modified HAQ (mHAQ as a continuous variable)
- Achievement of improvement from baseline to 6 month follow-up in HAQ of 0.22 (as a dichotomous variable)
- Change from baseline to 6 month follow-up HAQ (HAQ as a continuous variable)
- Change from baseline to 6 month follow-up modified DAS (mDAS as a continuous variable)
- Change from baseline to 6 month follow-up DAS ESR (as a continuous variable)
- Change from baseline to 6 month follow-up DAS CRP (as a continuous variable)
- Change from baseline to 6 month follow-up patient pain (as a continuous variable)
- Change from baseline to 6 month follow-up patient fatigue (as a continuous variable)
- Change from baseline to 6 month follow-up EQ-5D index (as a continuous variable)

- Modified ACR20, ACR50, ACR70

Please see Appendix for more details on the secondary outcomes.

Patients that switched to an agent other than tofa during the 6 months of follow-up will be considered for the continuous outcomes at the time of switch (rather than at 6 months).

In **Tables 2 and 3**, for the dichotomous primary and secondary outcomes, patients that discontinued or switched to an agent other than tofa will be considered as non-responders (e.g. did not achieve remission for patients that discontinued or switched prior to their 6 month visit).

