### Population for Overall Aim:

For the primary analysis comparing QD to BID patients, we will consider those patients who initiated tofa 5 mg BID on or after February 2016 and those that initiated tofa 11 mg QD after it became available in February 2016. Although the sample size will be smaller than if we consider all tofa 5 mg BID patients, the addition of those patients may introduce noise since there is the possibility that they could differ from the more recent initiators. Therefore, we will consider the cleaner cohort of all patients initiating tofa on or after February 2016.

In order to adequately measure the outcome, the initiators will also be required to have a follow-up visit at 6 months (+/- 3 months) after tofacitinib initiation.

The data cut to be used will be the most recent available.

With regards to dosing, patients can be categorized as follows:

QD dosing: once-daily tofacitinib 11mg

BID dosing: 5mg twice-daily

Other: other dosages including 10 mg and will also include not specified

Those in the "other" category will not be considered in these analyses.

The first initial look at the data has indicated that the tofa 5 mg BID group differs on some characteristics from the tofa 11 mg QD group. To account for these differences, in a second look at the data, we propose to consider models adjusted for no more than 10 covariates. This will provide a robust analysis, while preserving sample size. The full propensity score analysis will be done in the final look at the data when the sample size is large enough (as per preliminary power calculations on page 23).

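### The widened-window re-analysis lets a CDAI taken before month 3 count as six-month response, and all 116 patients it adds were seen outside the 3–9 month window

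*SAP*

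**What the plan says.** The outcome visit is fixed consistently in the main plan. Protocol 9.2.1 states: "Patients must have a follow-up visit at 6 months (+/- 3 months) after tofacitinib initiation". The SAP, under Population for Overall Aim, says that "the initiators will also be required to have a follow-up visit at 6 months (+/- 3 months) after tofacitinib initiation". Protocol 9.2 and 9.7 use the same window.

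The later SAP addendum, which moves to the 2019/08/31 registry version, changes this for one further re-analysis (Justification for proposed analyses). It first restates the present rule: "Where currently we only consider visits between 3 and 9 months as eligible to be the six-month follow-up visit". It then widens it by "considering any visit within the first year after initiation as eligible to be the six-month follow-up visit", and repeats the analyses "using this new sample of 689 patients".

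In the eligibility table of the same addendum (Table 2, Proposed Analyses), the row "Eligible six-month visit" holds "401 (66%) out of the 611 initiators of 11 mg QD, and 172 (67%) out of the 258 initiators of 5 mg BID". A separate row holds 116 patients (80 QD, 36 BID) who were seen in the first year but have no six-month visit.

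For binary outcomes, the SAP (Secondary Outcomes for Overall Aim) treats patients who stopped tofacitinib or changed to another agent as non-responders. Its example is remission: "did not achieve remission for patients that discontinued or switched prior to their 6 month visit".

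**The concern.** The widening removes the lower limit as well as the upper one. As worded, a visit well before month 3 may supply the CDAI that is then reported as six-month MCID response. The stop/switch rule can move with it. If it is applied only up to the visit used, a patient who meets MCID at month 1 and stops at month 2 is a responder, while a patient first seen at month 12 can be failed for a stop at any time in the year.

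The direction matters because the study hypothesis is similarity (Protocol 7; SAP Background). The addendum's repeated tables also include a non-inferiority table, and Protocol 12 says that results may go to a regulator. If the regimens differ and early visits do not yet show it, mixing those visits in makes the arms look more alike. A robustness check that can drift towards the hoped-for answer gives weaker support to the 3–9 month result.

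**Working it through.** **Reproducing the plan's figure.** Inputs are the rows of the addendum's Table 2.

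- All initiators: 113 + 67 + 116 + 573 = 869.
- Widened cohort: 573 + 116 = 689, which matches the SAP exactly. By arm: QD 401 + 80 = 481; BID 172 + 36 = 208.
- Every added patient therefore has first-year visits only before month 3 or after month 9.
- Off-window share: 116/689 = 16.8% (QD 80/481 = 16.6%; BID 36/208 = 17.3%).

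The addendum notes that a valid CDAI is still required at both times, so the number analysed will be somewhat below 689.

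**Effect on a true difference.** The 15-point difference and the 50% response rate come from the SAP power calculation. Let f be the share of the 116 seen too early to show any difference between arms. The documents do not give f, so the full range is shown. Assume that the 573 keep their 3–9 month visit and that the remaining added visits show the full 15 points.

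Observed difference = 15 × (1 − f × 116/689)

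| f | Observed difference (points) | Power, 481 vs 208 |
|---|---|---|
| 0 | 15.0 | 95.7% |
| 0.25 | 14.4 | 94.1% |
| 0.5 | 13.7 | 92.0% |
| 0.75 | 13.1 | 89.3% |
| 1 | 12.5 | 86.1% |

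Power uses the normal approximation for two proportions, 50% against 50% plus the difference, at two-sided 5% (the SAP does not state sidedness) and without matching. The 573-patient analysis (401 vs 172) has 91.8% power for 15 points. If early visits already show half of the effect, f is in effect halved: with all 116 early, the difference is 13.7.

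**No true difference.** With 50% response in both arms at six months and an early rate r common to both, the spurious difference at f = 1 is (80/481 − 36/208) × (r − 0.50). For r = 0.20 this is (−0.0068) × (−0.30) = 0.002, or 0.2 points. Widening cannot create a material difference between equal arms by this route.

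**If in-window visits can be displaced.** The readable sentence does not say that the 573 keep their visit. If a share s of all 689 were read too early, the difference would be 15 × (1 − s): 12.0 points at s = 20% and 7.5 at s = 50%. These values of s are assumptions.

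**Non-inferiority, illustration only.** The margin is not readable, so assume M = 10 to 15 points. SE = √(0.25/481 + 0.25/208) = 0.0415. One-sided error at the margin = 1 − Φ(1.96 − M × f × 0.168/0.0415). It is 2.5% at f = 0, about 4–5% at f = 0.5 and about 6–9% at f = 1.

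**The case against.** The strongest reply is that this is a supplementary re-run, and that is correct. Nothing readable replaces the 3–9 month definition. The same addendum separately repeats the analyses on the 573 and adds an analysis of all 869 that counts patients without a six-month visit as not achieving MCID. A reader might infer that the primary endpoint itself has been altered; the documents do not support that.

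A reader might also infer that the widening does pull the arms together. That does not follow either. It needs a true difference and early visits that miss it, and neither document gives a time-to-response figure. The 116 also include visits at 9 to 12 months, with longer exposure and more time for a stop to count as failure, which may act in the other direction. Questionnaires are completed about every six months (Protocol 9.4), so very early visits may be few. The off-window share is nearly equal by arm.

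Two further points stand in part. The sentence sits beside blacked-out text and cites a table that is not visible, so a rule for choosing among visits may exist there; this point rests only on what the readable sentence permits. On stops, the current window already misses a stop at month 4 after a visit at month 3, and the words about the six-month visit appear only in an example. Removing the floor enlarges that gap but does not create it.

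Power does not settle the matter. It falls below that of the 573-patient analysis once more than about half of the 116 are early, and power to detect a difference is a poor yardstick where the hoped-for finding is similarity.

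**Conclusion.** The point holds for the widened-window re-analysis only. By its stated rule, all 116 added patients (16.8% of 689) contribute an off-window visit, and a CDAI from before month 3 can be scored as six-month response. Later stops are missed if the non-responder rule ends at that visit.

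The possible shrinkage is limited: a true 15-point difference becomes something between 15.0 and 12.5 points. That range assumes that the 573 keep their visits, that early visits show none of the difference, and that the other added visits show all of it. The net direction cannot be settled without the split between visits before month 3 and visits at 9 to 12 months. This is worth correcting because any dilution would favour the similarity or non-inferiority conclusion, and this analysis is meant to test how robust the main result is.

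**What to change.** Amend the addendum wording and rerun the widened analysis as follows.

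- Keep the plan's own 3-month floor, so that the window is 3 to 12 months.
- Use the existing 3–9 month visit for the 573 who have one; otherwise use the visit nearest month 6.
- If the 0–12 month version on 689 is also shown, label it as a secondary sensitivity analysis.
- Apply one stop/switch non-responder rule to every patient in the analysis, for example stopped or switched before the later of month 6 and the outcome visit. A separate rule for the added patients would put two response definitions in one comparison.
- Report by arm how many of the 116 were seen before month 3 and how many at 9 to 12 months.

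The cost is a wording change and one rerun. The cohort will be somewhat smaller than 689, but patients seen only before month 3 remain in the all-869 analysis. The common stop rule may also reclassify some of the 573, so their result under that rule should be shown alongside to keep the comparison of windows clean.
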